#### 5.2.1.2. TTI-621 Prophylaxis

Prophylaxis for infusion-related reactions related to administration of TTI-621 will be given prior to infusion of TTI-621 on each day of scheduled treatment. Prophylaxis will consist of acetaminophen, anti-histamine and steroid as described in [Table 6](#). TTI-621 prophylaxis may be initiated prior to doxorubicin infusion on days when doxorubicin and TTI-621 are both given to accommodate site preference and scheduling. While steroid is not required for patients who have not experienced Grade 1 or 2 infusion-related reactions, the Investigator may incorporate steroid into the prophylaxis regimen.

**Table 6. Prophylaxis Regimen for TTI-621 to Reduce incidence and/or Grade of Infusion-Related Reaction**

Cycle Day of Treatment	Patients Requiring Premedication	Premedication	Administration
Cycle 1  Day 1 Day 8	All patients	80 mg methylprednisolone (oral) OR 20 mg dexamethasone (IV)	At least one hour prior to initiation of TTI-621 infusion
		650 – 1000 mg acetaminophen	At least 30 minutes prior to initiation of TTI-621 infusion
		Anti-histamine (e.g., 50 mg diphenhydramine)	
All subsequent cycles  Day 1 Day 8	All patients	650 – 1000 mg acetaminophen	At least 30 minutes prior to initiation of TTI-621 infusion
		Anti-histamine (e.g., 50 mg diphenhydramine)	
	Patients with Grade 3 or Grade 4 IRR in previous infusion 	80 mg methylprednisolone (oral) OR 20 mg dexamethasone (IV)	At least one hour prior to initiation of TTI-621 infusion
		650 – 1000 mg acetaminophen	At least 30 minutes prior to initiation of TTI-621 infusion
		Anti-histamine (e.g., 50 mg diphenhydramine)	

 Not required for patients who have not experienced Grade 3 or Grade 4 infusion-related reaction, but may be incorporated at the Investigator's discretion.

### 5.2.2. Doxorubicin

Doxorubicin will be administered with prophylaxis as described in [Section 5.2.1.1](#). In Cycle 1 through Cycle 6, doxorubicin will be used in accordance with standard of care with intravenous infusion at a dose of 75 mg/m^2 on Day 1 of each 21-day cycle for a maximum of six cycles (18 weeks). It is intended that each patient will receive six cycles of doxorubicin as fewer than six cycles provides less benefit to the patient compared to six or more cycles and guidelines for prophylaxis for prevention of doxorubicin-mediated dose-limiting neutropenia are provided in [Section 5.2.1](#). Investigators should consult the approved doxorubicin hydrochloride package insert for complete prescribing information (including warnings, precautions, contra-indications, adverse reactions and dose modifications) and may follow institutional procedures for the administration of doxorubicin. Doxorubicin should be made up to a volume of 100 mL and administered through a free-flowing catheter at 75 mg/m^2 by intravenous infusion in less than 60 minutes. The rate of infusion should be decreased if erythematous streaking along the vein proximal to the site of infusion or facial flushing occur.

In any cycle in which doxorubicin and TTI-621 are administered on the same day, doxorubicin treatment will precede administration of TTI-621. A delay before initiation of TTI-621 is not mandated.

As described below in [Section 5.2.3](#), it is intended that after completion of the planned six cycles of doxorubicin treatment, patients will transition to TTI-621 monotherapy and continue on monotherapy until progression. Patients who are unable to complete the planned six cycles of doxorubicin treatment

due to doxorubicin-related toxicity despite optimal prophylaxis and medical support but have received at least four cycles of combination treatment and are receiving clinical benefit may be eligible to revert to TTI-621 monotherapy with the next cycle (Cycle 5 or Cycle 6) after discussion with the Sponsor Medical Monitor provided the patient has not experienced disease progression and TTI-621 re-treatment guidelines as described in [Section 9.2.2](#) are met. The patient may be replaced or an additional patient may be enrolled for the purposes of having a heterogeneous population for evaluation of safety and clinical activity as described in [Section 6.7](#). The Investigator may consult with the Sponsor Medical Monitor on a patient-by-patient basis in the event that early evidence of doxorubicin-related toxicity arises.

The dose of doxorubicin should be calculated at the beginning of each cycle.

### 5.2.3. **TTI-621**

In Cycle 1 through Cycle 6, following administration of prophylaxis medications as described in [Section 5.2.1.2](#), TTI-621 will be administered by intravenous infusion over 120 minutes on Day 1 and Day 8 of each 21-day cycle. Beginning with Cycle 2, the infusion period may be reduced to 60 minutes at the investigator's discretion if the patient has not experienced infusion-related reaction during prior infusions.

For the purposes of safety decisions that guide cohort expansion and considerations of TTI-621 dose adjustment, the safety period will consist of the 21-day Cycle 1. During the dose escalation portion of the study, dosing of the first patient in a dosing cohort should be followed by a one-week observation period before enrollment of the second and subsequent patients within the dosing cohort.

After completion of Cycle 6, doxorubicin will be discontinued as per standard of care to avoid development of cumulative cardiac toxicity. However, treatment with TTI-621 monotherapy will continue until documentation of progression or unacceptable toxicity. Beginning with Cycle 7, following administration of prophylaxis medications as described in [Section 5.2.1.2](#), TTI-621 will be administered on Day 1 and Day 15 of 28-day cycles.

Patients who are unable to complete the planned six cycles of doxorubicin treatment due to doxorubicin-related toxicity despite optimal prophylaxis and medical support but have received at least four cycles of combination treatment and are receiving clinical benefit may be eligible to revert to TTI-621 monotherapy with the next cycle after discussion with the Sponsor Medical Monitor provided the patient has not experienced disease progression and TTI-621 re-treatment guidelines as described in [Section 9.2.2](#) are met.

The dose of TTI-621 is based on body weight and should be calculated at the beginning of each cycle and may be used throughout the cycle unless a patient experiences a >10% variation in weight within a cycle.

As described previously and presented below in [Table 7](#), three dose levels of TTI-621 are planned to be evaluated in combination with fixed-dose doxorubicin in a 3+3 study design in the dose escalation portion of the study. After review of emergent safety and other data from these dose levels, alternate TTI-621 dose levels may be evaluated to more fully understand safety or pharmacodynamics of TTI-621 in combination with doxorubicin, to more fully identify dose-limiting toxicities, to more clearly define the

maximum tolerated dose, and/or to optimize selection of the most appropriate dose(s) for evaluation in the expansion cohorts.

**Table 7. TTI-621 Dose Levels Planned for Evaluation in Combination With Doxorubicin**

Dose Level	TTI-621 Dose
1	0.2 mg/kg
2	0.7 mg/kg
3	2.0 mg/kg

During the dose expansion portion of the study, two dose levels of TTI-621 are planned to be evaluated in combination with fixed-dose doxorubicin in 31-patient expansion cohorts in a Simon two-stage model. The low dose of TTI-621 is anticipated to be 0.2 mg/kg and the high dose is anticipated to be the maximum of other TTI-621 dose levels evaluated in the dose escalation portion of the study, prospectively planned to be 2.0 mg/kg, but alternate dose levels may require evaluation and a different dose may be taken forward based after discussion with treating physicians and the Sponsor.

### 5.3. Criteria for Treatment Discontinuation

Patients may withdraw voluntarily from participation in the study or from study treatment at any time and for any reason. A patient's participation in the study may be terminated at his/her request or on the basis of the Investigator's clinical judgment. The reason for patient withdrawal will be documented in the source data and noted on the electronic case report form (eCRF).

At a minimum, all patients who discontinue study treatment, including those who refuse to return for a final visit, will be contacted for safety evaluations at the 30-Day Safety Follow-Up Visit.

If such withdrawal occurs, or if the patient fails to return for visits, the investigator must determine the primary reason for a patient's withdrawal from the study and record the information on the eCRF. If the reason for withdrawal is an adverse event, monitoring should continue until the outcome is evident. The specific event or test result(s) must be recorded in the eCRF. At the discretion of the Sponsor, patients may also be removed from the study.

It should be clearly documented in the source data whether patients withdrew their consent and will not enter the follow-up phase, including objective disease assessment for patients who withdrew from the study in the absence of objective disease assessment and survival, or if patients withdrew their consent for study treatment but will continue further participation in the follow-up phase.

Treatment may be continued until one of the following criteria applies:

- Completion of six cycles of doxorubicin treatment, at which point doxorubicin treatment must be discontinued but the patient may continue with TTI-621 monotherapy
- Objective (radiographic) disease progression: for patients with asymptomatic progression and in the absence of unacceptable toxicity, a consenting patient should continue treatment and a confirmation scan should be conducted at least 4 weeks later to document objective progression prior to removing patient from study treatment

- An unacceptable adverse event or safety observation, such as a persistent moderate toxicity that is intolerable to the patient, that is in the opinion of the Investigator clearly attributed to TTI-621
- An unacceptable adverse event or safety observation, such as a persistent moderate toxicity that is intolerable to the patient, that is in the opinion of the Investigator clearly attributed to doxorubicin and the patient has received fewer than four cycles of doxorubicin. A patient who has completed four cycles of doxorubicin treatment and experiences an adverse event that requires discontinuation of doxorubicin treatment despite optimal prophylaxis and medical support and who is receiving clinical benefit may be eligible to continue on study receiving TTI-621 monotherapy after discussion with the Sponsor Medical Monitor but may be replaced or an additional patient may be enrolled for the purposes of evaluating safety and activity of the combination of doxorubicin and TTI-621 as described in [Section 6.7](#).
- Unacceptable toxicity which in the opinion of the Investigator cannot be attributed to a specific study agent
- Any event which would cause TTI-621 or doxorubicin to be modified by more than two dose reductions or to be held for more than 21 days from the last administered dose and is not attributable to a particular agent of the combination regimen; exception is made for patients who are receiving meaningful clinical benefit and the investigator feels, with Sponsor Medical Monitor concurrence, that continued treatment is in the best interest of the patient
- Any treatment-related adverse event that is deemed life-threatening, regardless of grade; exception is made for patients in whom the life-threatening adverse event is attributed to doxorubicin despite optimal prophylaxis and medical support and the patient is receiving clinical benefit and the patient has received at least four cycles of doxorubicin treatment and the investigator feels, with Sponsor Medical Monitor concurrence, that continuation with TTI-621 monotherapy would be reasonable and the patient meets guidelines for re-treatment with TTI-621 as described in [Section 9.2.2](#)
- Discontinuation of TTI-621 treatment
- An intercurrent illness or change in the patient's condition that renders the patient unsuitable for further treatment in the opinion of the Investigator; exception may be made for patients in whom the intercurrent illness or change in condition is thought to render the patient ineligible for continued treatment with doxorubicin despite optimal prophylaxis and medical support and the patient has received at least four cycles of doxorubicin and is receiving clinical benefit and the investigator feels, with Sponsor Medical Monitor concurrence, that continuation with TTI-621 monotherapy would be reasonable and the patient meets criteria for TTI-621 re-treatment as described in [Section 9.2.2](#)
- Significant non-compliance with protocol
- Pregnancy
- Withdrawal of consent (patient may participate in long-term assessment of survival and disease status [if withdrawn prior to documentation of objective disease progression] if consent for this portion of the study is not withdrawn)
- Subject is lost to follow-up
- Termination of the study by the sponsor

At the investigator's discretion and in agreement with the Sponsor Medical Monitor, treatment after objective disease progression may continue for a patient who is clinically stable and receiving meaningful clinical benefit and the investigator feels it is in the patient's best interest to continue treatment. The reason for continuing treatment must be thoroughly discussed, agreed with the Sponsor Medical Monitor, and clearly documented in the study files.

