	
The Investigator should withdraw a patient from all study-related treatment for any of the following reasons:
 

• An unacceptable adverse event or safety observation, such as a persistent moderate toxicity that is intolerable to the patient, that is in the opinion of the Investigator clearly attributed to TTI-621

• An unacceptable adverse event or safety observation, such as a persistent moderate toxicity that is intolerable to the patient, that is in the opinion of the Investigator clearly attributed to doxorubicin and the patient has received fewer than four cycles of doxorubicin. A patient who has completed four cycles of doxorubicin treatment and experiences an adverse event that requires discontinuation of doxorubicin treatment despite optimal prophylaxis and supportive care and is receiving clinical benefit may be eligible to continue to TTI-621 monotherapy with the next cycle (Cycle 5 or Cycle 6) after discussion with the Sponsor Medical Monitor and provided the patient has not experienced disease progression and TTI-621 re-treatment guidelines as described in Section 9.2.2 are met; the patient may be replaced or an additional patient may be enrolled for the purposes of having a heterogeneous population for evaluation of safety and clinical activity as described in Section 6.7.

• Any event which would cause TTI-621 or doxorubicin to be modified by more than two dose reductions or to be held for more than 42 days from the last administered dose and is not attributable to a particular agent of the combination regimen; exception is made for patients who are receiving meaningful clinical benefit and the investigator feels, with Sponsor Medical Monitor concurrence, that continued treatment is in the best interest of the patient

• Any treatment-related adverse event that is deemed life-threatening, regardless of grade; exception is made for patients in whom the life-threatening adverse event is attributed to doxorubicin and has occurred despite optimal prophylaxis and medical support and the patient is receiving clinical benefit and has received at least four cycles of doxorubicin treatment and the investigator feels, with Sponsor Medical Monitor concurrence, that continuation with TTI-621 monotherapy would be reasonable; the patient may be replaced or an additional patient enrolled for the purposes of having a heterogeneous population for evaluation of safety and clinical activity as described in Section 6.7.

• Documentation of objective (radiographic) disease progression; for patients with asymptomatic progression and in the absence of unacceptable toxicity, the patient should continue treatment and a confirmation scan should be

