**Table 11. Definition of Infusion-Related Reaction by CTCAE Grade**

CTCAE Grade	Definition
Grade 1 IRR	Mild transient reaction; infusion interruption not indicated; intervention not indicated
Grade 2 IRR	Therapy or infusion interruption indicated but responds promptly to symptomatic treatment (e.g., anti-histamines, NSAIDS, narcotics, IV fluids); prophylactic medications indicated for $\leq$ 24 hours
Grade 3 IRR	Prolonged (i.e., not rapidly responsive to symptomatic medication, brief interruption of infusion, or both); recurrence of symptoms following initial improvement; hospitalization indicated for clinical sequelae
Grade 4 IRR	Life-threatening consequences; urgent intervention indicated

Note: An acute infusion reaction may occur with an agent that causes cytokine release (e.g., monoclonal antibodies or other biological agents). Signs and symptoms usually develop during or shortly after drug infusion and generally resolve completely within 24 hours of completion of infusion. Signs/symptoms may include: allergic reaction/hypersensitivity (including drug fever); arthralgia (joint pain); bronchospasm; cough; dizziness; dyspnea (shortness of breath); fatigue (asthenia, lethargy, malaise); headache; hypertension; hypotension; myalgia (muscle pain); nausea; pruritis/itching; rash/desquamation; rigors/chills; sweating (diaphoresis); tachycardia; tumor pain (onset or exacerbation of tumor pain due to treatment); urticaria (hives, welts, wheals); vomiting.

As described in [Section 5.2.1](#), prophylaxis is required prior to infusion of TTI-621. Patients will be closely monitored for signs and symptoms of hypersensitivity or allergic reactions. Guidelines for management of infusion-related reactions are presented in [Table 12](#).

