**Table 12. Management of Infusion-Related Reactions Associated with TTI-621 Administration**

CTCAE Grade	Management Guidelines
Grade 1 Infusion-Related Reaction	
 
The infusion may be stopped or continued at a reduced (50%) infusion rate at the discretion of the Investigator.
 
If symptoms resolve, the infusion can be re-started or increased, as tolerated, to the baseline rate.
 
The patient may receive appropriate further treatment for infusion-related reaction if clinically indicated per the site's standard practice for management of IRR.
 

Grade 2 Infusion-Related Reaction	
 
The infusion should be stopped.
 
The patient should receive appropriate further treatment with an anti-histamine and/or acetaminophen if clinically indicated per the site's standard practice for management of IRR. Further medications can be administered if necessary.
 
Once symptoms have resolved or reduced to Grade 1, the infusion can be continued at a reduced (50%) infusion rate. If after one hour the patient's symptoms do not return and vital signs are stable, the infusion rate may be increased every 30 minutes, as tolerated, to the baseline rate.
 

Grade 3 Infusion-Related Reaction	
 
The infusion should be stopped promptly.
 
The patient must receive appropriate treatment with an anti-histamine and/or acetaminophen and/or methylprednisolone or equivalent and, if necessary, further medications (i.e., epinephrine, bronchodilator).
 
Only after the complete resolution to Grade <math>\leq 1</math>, and after having received appropriate prophylactic medication(s) as described above, the infusion may be resumed at an infusion rate of 25%. If after one hour the patient's symptoms do not return and vital signs are stable, the infusion rate may be increased to a maximum of 50%.
 
If after the resumption of infusion, symptoms return (irrespective of grade), the infusion must be stopped and the infusion tubing should be disconnected.
 
The duration of infusion may be prolonged in order to ameliorate IRR but TTI-621 dose does not require reduction.
 

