Grade 4 Infusion-Related Reaction	
 
The infusion should be stopped promptly and the infusion tubing should be disconnected.
 
The patient should receive appropriate treatment with an anti-histamine and/or acetaminophen and/or methylprednisolone (or equivalent) and, if necessary, further medications (i.e., epinephrine, bronchodilator).
 
After discussion with the Sponsor Medical Monitor, the patient must not receive further infusions of TTI-621 if TTI-621 is judged by the Investigator to be the cause of the infusion-related reaction and the investigator feels that implementation of alternative or more aggressive prophylaxis would not be sufficient.
 

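### Section 5.3 and the Synopsis stop treatment after a life-threatening reaction attributed to TTI-621, while Section 9 (Tables 12, 14, 15 and 21) leaves re-treatment open, and nothing says which governs

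*Protocol*

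**What the plan says.** **Stopping rules.** The list in Protocol Section 5.3 opens with "Treatment may be continued until one of the following criteria applies". One criterion is a treatment-related adverse event "deemed life-threatening, regardless of grade; exception is made for patients in whom the life-threatening adverse event is attributed to doxorubicin despite" adequate prophylaxis and support. That exception also requires at least four doxorubicin cycles, clinical benefit, Sponsor Medical Monitor concurrence and fulfilment of the TTI-621 re-treatment guidelines. Section 5.3 separately lists discontinuation of TTI-621 as a criterion. The Synopsis opens its list with "The Investigator should withdraw a patient from all study-related treatment for any of the following reasons" and carries the same doxorubicin-only carve-out: "exception is made for patients in whom the life-threatening adverse event is attributed to doxorubicin and has occurred despite" adequate prophylaxis and support. Neither place has an exception for an event attributed to TTI-621.

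**Grading.** Table 11 defines a Grade 4 IRR as "Life-threatening consequences; urgent intervention indicated".

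**Management guidelines (Section 9).**
- Table 12, Grade 4 row: after discussion with the Medical Monitor, "the patient must not receive further infusions of TTI-621 if TTI-621 is judged by the Investigator to be the cause" of the reaction and "the investigator feels that implementation of alternative or more aggressive prophylaxis would not be sufficient".
- Table 14 (non-hematologic events): discontinuation is to be considered after a Grade 4 event, but TTI-621 can resume once re-treatment criteria are met if the investigator judges that best for the patient. IRR is not among its listed exceptions.
- Table 15 (other treatment-related events): a Grade 4 event ends TTI-621 unless there is clinical benefit, recovery to baseline and a physician's recommendation to continue at a lower dose or on a changed schedule.
- Table 21 (attribution not possible): after a first non-hematologic event of Grade 3 or higher, delay, then restart both drugs one dose level lower. It excludes an IRR only when the described prophylaxis was not given.
- Table 6 (Section 5.2.1.2) sets premedication for later TTI-621 infusions in patients whose previous infusion caused a Grade 3 or Grade 4 IRR.

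**The concern.** The two parts of the protocol give opposite answers to one question: may a patient receive TTI-621 again after a life-threatening reaction to it? A site treating an acute reaction would naturally open Table 12, whose Grade 4 row does not point to Section 5.3. A site working through the discontinuation criteria would stop. At stake are patient safety and consistent handling between sites. Under one reading a patient is re-exposed to a drug that has already caused a life-threatening reaction; under the other, a patient who might have been re-challenged loses treatment.

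**Working it through.** The plan states no figure to reproduce. The check is a comparison of texts, followed by a bound on frequency.

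**Step 1. Does the event meet the stopping rule?** The trigger is a treatment-related event deemed life-threatening. Table 11 defines Grade 4 IRR by life-threatening consequences, so assigning the grade ordinarily makes that judgement.

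**Step 2. Is it excepted?** Only events attributed to doxorubicin are. Two other passages in Section 5.3 do not help. The clinical-benefit exception belongs to the bullet on dose reductions and holds not attributable to one agent. The closing paragraph concerns treatment after disease progression.

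**Step 3. What does Section 9 say for the same patient?** Let A = TTI-621 judged to be the cause, and B = stronger prophylaxis felt to be insufficient. Table 12 bars re-infusion only when A and B both hold.

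| Situation after a Grade 4 IRR | Section 5.3 and Synopsis | Section 9 |
|---|---|---|
| A and B | Stop | Table 12: barred (agrees) |
| A, not B | Stop, no exception | Table 12: bar not triggered |
| Treatment-related, drug not identifiable, prophylaxis given | Stop, no exception | Table 21: delay, then restart at reduced doses |

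The second and third rows conflict. Table 12 never says that infusion may restart after Grade 4, whereas its Grade 3 row does: "the infusion may be resumed at an infusion rate of 25" percent. Re-infusion after Grade 4 is therefore open by implication only. Even so, condition B has no function unless re-infusion is sometimes allowed.

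**Step 4. Is the conflict confined to Table 12?** No. Tables 14 and 15 expressly permit resumption or continuation after Grade 4 events and do not set apart those deemed life-threatening. Table 6 reads as expecting re-infusion after a Grade 4 IRR. The Table 21 case is realistic because both drugs are given on Day 1 of Cycles 1 to 6.

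**Step 5. Does any text rank the sections?** None does. Section 9 calls its contents guidelines but does not yield to Section 5.3.

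**Step 6. How often could this arise?** Grade 4 IRRs are not reported separately for TTI-621-01 (Section 3.5.2.1.2, N = 235).
- Upper bound from Table 2, all treatment-related IRRs of Grade 3 or higher: 8/235 = 3.4%.
- Upper bound from Table 3, all treatment-related serious IRRs: 7/235 = 3.0%. This assumes that study counted every life-threatening event as serious, as Section 13.1.2 does here.
- Lower bound: 0/235 = 0%.

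Section 3.8.1 says reactions there occurred despite antihistamine and acetaminophen, and that this study adds a steroid, so the rate here may be lower.

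**The case against.** **The word 'deemed'.** Section 5.3 acts on a judgement that it separates from grade, and the protocol does not treat Grade 4 as a stop in itself: Table 13, for example, lets TTI-621 resume after Grade 4 neutropenia. A Grade 4 IRR that needed urgent intervention might be held not to be life-threatening, and Table 12 would then contradict nothing. This stands in part. It limits the conclusion to the natural reading of Table 11. It does not remove the conflict, because Table 11 names life-threatening consequences first and tells no one to make a second determination.

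**Section 9 is only guidance, or the specific rule prevails.** Neither order of precedence is written down. The drafters gave doxorubicin-attributed events a detailed exception and gave TTI-621-attributed events none, which makes an unstated one hard to read in.

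**The Medical Monitor will settle it.** The Grade 4 row asks for discussion, not concurrence, and condition B rests on the investigator's view. The discussion should reduce variation between sites, but Section 5.3 gives the Medical Monitor no route to continue such a patient.

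**The sponsor may intend re-challenge.** Tables 6, 12, 14 and 15 all contemplate discretion after Grade 4. This stands: the documents do not show which rule was meant to prevail, so the fix offers both.

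**Conclusion.** The concern holds. On the natural reading of Table 11, a Grade 4 IRR attributed to TTI-621 falls under a stopping rule with no applicable exception, while Section 9 leaves re-treatment open: by implication in Table 12, expressly in Tables 14 and 15 for Grade 4 events generally, and through a dose-reduced restart in Table 21 when attribution is not possible.

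A reader might infer more than the documents support:
- That Table 12 authorises re-infusion after Grade 4. It has no express permission.
- That every Grade 4 event requires withdrawal. The trigger is an event deemed life-threatening, not the grade.
- That one Table 12 row is the whole problem. Editing only that row would leave Tables 6, 14, 15 and 21 in tension with Section 5.3.
- That the trial's inference is compromised. The Simon thresholds and error rates do not depend on this rule.

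The size is small in frequency: 0 to 8 of 235 in the earlier study, with zero possible and no projection made for this trial. The point merits correction because it governs re-exposure after a life-threatening reaction. SAP Section 4.3.2 describes Cohort C enrollment in the past tense, so the benefit may be limited to patients still receiving TTI-621.

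**What to change.** In one protocol amendment, by default letting the stricter rule govern:

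1. State in Section 9.2.3 that Section 5.3 governs any treatment-related event deemed life-threatening and overrides Tables 12, 14, 15 and 21.
2. In the Grade 4 row of Table 12, delete the second condition (that "the investigator feels that implementation of alternative or more aggressive prophylaxis would not be sufficient", with its joining 'and') and add a reference to Section 5.3.
3. Footnote the Grade 4 entry in Table 6 as applying only to patients allowed to continue under Section 5.3. The entry should stay: a patient with a Grade 4 IRR attributed to doxorubicin after at least four cycles may still continue TTI-621.

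If the sponsor intends to allow re-challenge, instead add to the life-threatening-event bullets in Section 5.3 and the Synopsis an explicit exception for TTI-621-attributed events. It should require clinical benefit, recovery to re-treatment criteria and Sponsor Medical Monitor concurrence, and be cross-referenced from Tables 12, 14, 15 and 21.

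Either route costs wording only, with no new data or visits and no change to the sample size.
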